1. LIST OF ABBREVIATIONS

Abbreviation	Definition
ABC	Advanced breast cancer
AE	Adverse event
AEM	Adverse event monitoring
ADL	Activities of Daily Living
CAN	Canada
CBC	Complete blood count
CDK	Cyclin Dependent Kinase
cfDNA	Circulating cell free deoxyribonucleic acid
CGA	Comprehensive Geriatric Assessment
CI	Confidence interval
CIOMS	Council for International Organizations of Medical Sciences
eCRF	Electronic case report form
DNA	Deoxyribonucleic acid
ECOG	Eastern Cooperative Oncology Group
EDC	Electronic data capture
EDP	Exposure during pregnancy
EMA	European Medicines Agency
ENCePP	European Network of Centres for Pharmacoepidemiology and Pharmacovigilance
EORTC QLQ-C30	European Organisation for the Research and Treatment of Cancer Quality of Life Questionnaire Core 30
ER	Estrogen receptor
ER+	Estrogen receptor positive
ESMO	European Society for Medical Oncology
FDA	Food and Drug Administration
GA	Geriatric Assessment
GEP	Good Epidemiological Practice
GPP	Good Pharmacoepidemiology Practices
HER2-	Human epidermal growth factor receptor 2 negative
HR	Hazard ratio
HR+	Hormone receptor positive
IEA	International Epidemiological Association
IEC	Independent ethics committee
IRB	Institutional review board
ISMF	Investigator Site Master File
ISPE	International Society for Pharmacoepidemiology
ISPOR	International Society for Pharmacoeconomics and Outcomes Research
MBC	Metastatic breast cancer
NCCN	National Comprehensive Cancer Network
NIS	Non-interventional study
PFS	Progression free survival
PR+	Progesterone receptor positive

Palbociclib
A5481082 NON-INTERVENTIONAL STUDY PROTOCOL
FINAL AMENDMENT 1, 02AUG2017

PRO	Patient reported outcomes
PV	Pharmacovigilance
QOL	Quality of life
RB	Retinoblastoma
RNA	Ribonucleic acid
SAE	Serious adverse event
SAP	Statistical analysis plan
SAS	Statistical analysis system
SIOG	Society of Geriatric Oncology
SOC	Standard of care
SOP	Standard operating procedure
US	United States

3. ABSTRACT

POLARIS: Palbociclib in Hormone Receptor Positive Advanced Breast Cancer: A Prospective Multicenter Non-Interventional Study (NIS)

BACKGROUND: Palbociclib is a novel cyclin dependent kinase (CDK)4/6 inhibitor approved in the United States (US) and Canada (CAN) in combination with certain endocrine therapies for hormone receptor positive (HR+)/human epidermal growth factor receptor 2 negative (HER2-) advanced breast cancer (ABC). With the introduction of this first in class therapy, it is important to understand palbociclib treatment patterns in routine clinical practice in the US and CAN; and as a result, the evolving treatment landscape of ABC. This study will provide prospective, observational data in the real world setting to contribute to the knowledge of palbociclib in ABC disease management and the new ABC treatment paradigm.

OBJECTIVES: The objectives of this prospective NIS of palbociclib in ABC treatment are to describe and analyze palbociclib prescribing and treatment patterns in routine clinical practice, clinical outcomes, metastatic breast cancer (MBC) treatment sequencing prior to, during, and after palbociclib, patient quality of life, geriatric specific assessment; and **CCI**

STUDY DESIGN: A prospective, observational, NIS.

POPULATION: HR+/HER2- ABC patients whose treatment decision with palbociclib has been made by their treating physician and who meet the eligibility criteria will be invited to participate in the study.

DATA SOURCES: This prospective, observational study will be conducted according to each site's routine clinical practice. Data will be captured using a web-based collection tool.

STUDY SIZE: Approximately 1500 patients from approximately 100 US sites and 10 CAN sites (community and academic) will be enrolled. Study duration will consist of observation of patients on palbociclib treatment and approximately 3 years of follow-up post each patient's end of treatment with palbociclib, or until patient withdrawal from the study or death.

DATA ANALYSIS: Descriptive statistics will be used to summarize all endpoints.

4. AMENDMENTS AND UPDATES

Amendment number	Date	Substantial or administrative amendment	Protocol section(s) changed	Summary of amendment(s)	Reason
1	02AUG 2017	Substantial	Study Information Section 1. List of Abbreviations Section 3. Abstract Section 6. Background and Rationale Section 7. Research Objectives and Questions Section 8. Research Methods Section 12. References	Study Information: Research objectives and questions updated to include clinical outcomes as a main objective. Section 1. List of Abbreviations: Canada added to the table. Section 3. Abstract: Updated to include approximately 10 Canadian sites, and added clinical outcomes as a main objective. Section 6. Background and Rationale: Updated to include Canada and provide background information on Canadian Breast Cancer Statistics. Section 7. Research Objective and Question: Main research objectives updated to include clinical outcomes. Section 8. Research Methods: Updated to include approximately 10 sites in Canada. Section 8. Table 1: Data Entry Schedule: Footnotes updated to clarify physician MBC treatment selection survey. CC1 [REDACTED] [REDACTED] clarify CBC data collection, and clarify reporting of adverse event data. CC1 [REDACTED] [REDACTED] [REDACTED] [REDACTED] [REDACTED] [REDACTED] Section 12. References: References updated.	Study amended to include Canada for participation, specify clinical outcomes as a research main objective, and update the data entry table to clarify safety reporting time period. CC1 [REDACTED] potential analysis and clarify CBC data entry and references were updated.

5. MILESTONES

Milestone	Planned date
Start of data collection	16Dec2016
End of data collection	16Dec2021
Final study report	15NOV2022

6. RATIONALE AND BACKGROUND

6.1. Breast Cancer

Breast cancer remains the most common cancer in women worldwide, with 1.6 million new cases diagnosed and a half a million deaths reported annually. In the US, an estimated 246,660 new cases of invasive breast cancer, and an additional 61,000 new cases of in situ breast cancer, are expected to be diagnosed in 2016 (American Cancer Society, 2016). Breast cancer is ranked the second highest cause of cancer death in American women (American Cancer Society, 2016) and is the third highest cause of cancer death overall, behind lung cancer and colon/rectum cancer, with 40,450 estimated deaths in the US in 2016 (Howlader et al 2016). Breast cancer represents about 29% of all new cancer cases and 14% of all cancer deaths in women in the US (American Cancer Society, 2016). From 2003 to 2012, breast cancer incidence rates in the US were stable in white women and increased slightly, at rate of 0.3% per year, in black women. While death rates declined over the same time period (by 1.9% in white women and 1.4% in black women), due to early detection and treatment (American Cancer Society, 2016), breast cancer still remains a major health issue in the US. Statistics for breast cancer in males are also notable: 2,600 new cases are expected to be diagnosed in the US in 2016, with 440 estimated deaths (American Cancer Society, 2016).

According to latest figures from the Canadian Cancer Society (Canadian Cancer Society's Advisory Committee on Cancer Statistics, 2016), 1 in 9 Canadian women are expected to develop breast cancer in their lifetime, with 25,700 expected new cases in 2016. Breast cancer is the second most common cause of cancer death in Canadian women, accounting for 13% of all cancer deaths in women, and is the third most common cancer in Canada (CAN), accounting for 13% of all cancers and 26% of cancers among women. Consistent with data from the US, breast cancer incidence rate in CAN stabilized from 2004 through 2010 and the death rate due to breast cancer has fallen from a peak of 41.7 deaths per 100,000 in 1987 to a projected rate of 23.4 deaths per 100,000 in 2016 (Canadian Cancer Society's Advisory Committee on Cancer Statistics, 2016).

Approximately 80% of breast cancers expressed estrogen receptor (ER), progesterone receptor (PR), or both. Endocrine therapy is the mainstream treatment for the HR+ cancers. Currently, first-line treatment in the ER+/HER2-ABC postmenopausal population typically includes endocrine therapies, such as letrozole, anastrozole, exemestane, fulvestrant, and tamoxifen with time to progression and prolongation of progression free survival (PFS) ranging from 5 to 15 months (Cardoso, 2012; Bergh, 2012; Mehta, 2012). These treatment options are supported by clinical practice guidelines published by the European Society for Medical Oncology (ESMO) and the National Comprehensive Cancer Network (NCCN) as preferred first-line options in patients who are antiestrogen naïve or who are more than 2 years from previous antiestrogen therapy and do not have extensive visceral involvement (Cardoso, 2012; NCCN, 2016). Single-agent treatment with an aromatase inhibitor or tamoxifen has shown limited clinical benefit (Baselga et al 2012; Klijn et al 2000). The selective ER degrader fulvestrant has modest activity in this population of patients (Di Leo et al 2010, 2014) and the development of effective therapies that can address resistance to endocrine therapy is of clinical importance.

6.2. Palbociclib

In vitro evidence suggests that breast cancer that has developed resistance to prior endocrine therapy remains dependent on cyclin D1–CDK4/6 to promote proliferation (Miller et al, 2011; Thangavel et al, 2011). Palbociclib is an orally bioavailable small-molecule inhibitor of CDK4 and CDK6, with a high level of selectivity for CDK4 and CDK6 over other cyclin-dependent kinases (Toogood et al, 2005). Palbociclib inhibits CDK4 and CDK6 in vitro, resulting in loss of retinoblastoma (RB)1 phosphorylation. It has high activity in hormone-receptor–positive breast-cancer cell lines and is synergistic in combination with endocrine therapies (Finn et al, 2009).

In a phase 1/2 study, PALOMA-1 (Finn et al, 2015), patients were randomized to a 1:1 ratio to receive palbociclib + letrozole or letrozole alone. The median PFS was 20.2 months with palbociclib + letrozole and 10.2 months with letrozole alone (Hazard ratio [HR]=0.488; $P=0.0004$). In terms of the safety profile, Grade 3/4 neutropenia was significantly higher in patients receiving palbociclib + letrozole compared with letrozole alone (54% vs 1%). Additionally, the rate of Grade 3/4 leucopenia (19% vs 0%) and fatigue (4% vs 1%) were also higher with palbociclib + letrozole. No cases of febrile neutropenia or neutropenia-related infections were reported in the study (Finn et al, 2015).

A phase 3 study, PALOMA-2 (Finn et al, 2016), was conducted with 666 post-menopausal women without prior systemic therapy for ER+/HER2– ABC. Patients were randomized to a 2:1 ratio to receive palbociclib + letrozole or placebo + letrozole. The median PFS was 24.8 months with palbociclib + letrozole and 14.5 months with placebo + letrozole (HR=0.58; 95% confidence interval [CI] 0.46, 0.72, $P<0.000001$). Common adverse events (AEs; all grades) with palbociclib + letrozole vs placebo + letrozole were neutropenia (75% vs 5%), fatigue (41% vs 23%), nausea (25% vs 13%), arthralgia (33.3% vs 33.8%), and alopecia (32.9% vs 15.8%). Grade 3/4 neutropenia occurred in 54% of patients; other AEs were of Grade 1 severity. Febrile neutropenia was seen only with palbociclib + letrozole (2.5%). Permanent discontinuation due to AEs occurred in 9.7% of patients receiving palbociclib + letrozole vs 5.9% receiving placebo + letrozole. PALOMA-2 confirmed the significant clinical benefit and safety of palbociclib + letrozole in ER+/HER2– ABC patients who had not received prior systemic therapy for their advanced disease (Finn et al, 2016).

Another phase 3 study, PALOMA-3, was conducted with 521 patients with advanced HR+/HER2– patients that had relapsed or progressed during prior endocrine therapy (Turner et al, 2015). Patients were randomized to a 2:1 ratio to receive palbociclib + fulvestrant or placebo + fulvestrant. The median PFS was 9.2 months (95% CI, 7.5, upper limit not estimable) with palbociclib + fulvestrant and 3.8 months (95% CI 3.5, 5.5) with placebo + fulvestrant (HR for disease progression or death, 0.42; 95% CI 0.32, 0.56; $P<0.001$). The most common grade 3 or 4 AEs in the palbociclib+fulvestrant group were neutropenia (62.0%, vs. 0.6% in the placebo + fulvestrant group), leukopenia (25.2% vs. 0.6%), anemia (2.6% vs. 1.7%), thrombocytopenia (2.3% vs. 0%), and fatigue (2.0% vs. 1.2%). Febrile neutropenia was reported in 0.6% of patients in each treatment group. The rate of discontinuation due to AEs was 2.6% vs. 1.7% (Turner et al, 2015).

Estrogen receptor-positive breast cancer is biologically heterogeneous. Although palbociclib clinical trial results are very promising, it is also recognized that not all patients may respond to palbociclib treatment, and palbociclib treatment does come with mechanism based toxicities. **CCI**

[REDACTED]

[REDACTED]

[REDACTED]

6.3. EORTC QLQ-C30

In recent years, progress has been made in using patient-reported outcome (PRO) measures to determine how patients experience their disease over the course of treatment, receive aftercare, and live with cancer as a chronic condition. There is a growing demand for routine monitoring of PROs to complement clinical data with the patient's perspective (Wintner et al, 2016) and to evaluate cancer treatment-related symptoms, which are common and often underreported (American Cancer Society 2016).

The European Organisation for the Research and Treatment of Cancer Quality of Life Questionnaire Core 30 (EORTC QLQ-C30) (Luckett et al 2011; Velikova et al, 2012; Wintner et al, 2016) is widely used to assess changes in quality of life for patients undergoing treatment for cancer. The EORTC QLQ-C30 is a 30-item questionnaire composed of five multi-item functional subscales (physical, role, cognitive emotional, and social functioning), three multi-item symptom scales (fatigue, nausea/vomiting, and pain), a global health/quality of life (QOL) subscale, and six single items assessing other cancer-related symptoms (dyspnea, sleep disturbance, appetite, diarrhea, constipation, and the financial impact of cancer), with responses based on recall during the past week (see Annex 1: Stand Alone Documents: EORTC QLQ-C30). The EORTC QLQ-C30 has been translated and linguistically validated into more than 60 languages (Velikova et al, 2012).

6.4. Geriatric Assessments

The median age at diagnosis of breast cancer in the US is 62 years, and the majority of women who die of breast cancer in the US are age 65 years and older (median: 68 years) (Howlader et al 2016). In CAN, the majority (51%) of breast cancers occur in women 50 to 69 years of age, and approximately 32% of breast cancers are diagnosed in females aged 70 and over (Canadian Cancer Society, 2016). The US population that is 80 years and older is rapidly expanding—from 9 million members in 2001 to an anticipated 30 million members by 2050 (United Nations, 2001; Shachar et al, 2016a,b). As a group, older adults are more vulnerable to the adverse effects of cancer when compared with younger patients, in large part because of their higher incidence of comorbidities, their frequent use of many concomitant medications, and age-associated physiologic changes that may affect organ function (Schachar et al 2016b). To understand the population better in order to provide more appropriate treatment options, in 2005 the International Society of Geriatric Oncology (SIOG) recommended the use of geriatric assessment in cancer patients aged 70 years or older (Decoster et al, 2015). It is believed that the plausible data from the geriatric assessment can help devise treatment strategy and maximize the benefit of treatment outcome. Based on the lack of information in this population (Schachar et al 2016a,b), it is intended that the geriatric assessment effectively addresses these and many other areas of

geriatric care that are crucial to the successful treatment and prevention of disease and disability in older people, especially in cancer patients.

The comprehensive geriatric assessment (CGA) is a multidimensional, multidisciplinary assessment designed to evaluate an older person's functional ability, physical health, cognition and mental health, and socioenvironmental circumstances (Elsawy and Higgins, 2011). CGA has been found to improve treatment outcomes in older patients in the areas of prediction of treatment related toxicities, treatment adherence, quality of life, treatment decision making, and overall survival (Owusu and Berger 2014). A lack of consensus remains as to which domains to be included in a CGA, and what subsequent assessment and interventions to be used. CGA is time consuming and makes implementation in busy clinical practice challenging (Hurria et al, 2005).

Several screening tools have been developed as brief assessment in older patients, to identify vulnerable patients in need of full CGA. These tools may also have prognostic or predictive value in the outcome measures of treatment related toxicity, functional decline and survival (Decoster et al, 2015). One of the most studied screening tools for elderly cancer patients is G8 Screening Tool, which will be completed in the current protocol only for patients equal to or greater than 70 years of age at the time of study enrollment. The G8 was introduced by Bellera et al. in 2012 as a physician-assessed tool to identify geriatric cancer patients for whom the administration of a time consuming comprehensive geriatric assessment would be beneficial. Patients can fill in this instrument with the assistance of a healthcare professional (Soubeyran et al, 2014). The G8 has shown high sensitivity and specificity among different screening tools (Decoster et al, 2015; Hentschel et al, 2016; Martinez-Tapia et al, 2016). Eight items are included, based mainly on nutritional status, with responses based on recall for up to 3 months. The G8 has been found predictive for chemotherapy-related toxicity (Stokoe et al, 2012.) and prognostic for survival in mostly solid tumors (Liuu et al, 2012; Kenis et al 2014). A score of less than or equal to 14 indicates further full assessment may be needed (Bellera et al, 2012).

An additional screening tool that will be completed only for patients equal to or greater than 70 years of age at the time of study enrollment is activities of daily living (ADL). Although not specifically designed for geriatric patients, ADL assesses basic self-care skills to maintain independence in home (bathing, dressing toileting, feeding oneself, maintain continent, transferring from bed/chair). Studies have shown that functional status predicts survival, chemotherapy toxicity, postoperative morbidity, mortality (Eberhardt et al, 2006; Maione et al, 2005). Correlation of ADL dependence and outcome is less established in studies of older patients receiving outpatient oncology care, likely because there is a low proportion of patients requiring this degree of assistance (Extermann and Hurria, 2007).

Elderly patients have not been significantly represented in clinical trials for targeted therapies for breast cancer, including those that led to registration of palbociclib (Shachar et al, 2016). Additional research on older patients being treated with palbociclib, such as in routine clinical practice setting, may generate data to bridge the gap in understanding the tolerability and outcomes in this venerable patient population, commonly with comorbidities and declining general health due to aging.

6.5. Summary

Palbociclib is a novel CDK4/6 inhibitor approved in US and CAN in combination with certain endocrine therapies for HR+/HER2- ABC. With the introduction of this first in a new class of drugs, it is important to understand palbociclib treatment patterns in routine clinical practice in the US and CAN and, as a result, the evolving treatment landscape of ABC. It is important to understand real-world practice patterns and patient reported outcomes as clinical trial populations may not be representative of the target populations of patients given the enrollment criteria in clinical trials coupled with the focus on a single line of therapy. This study will provide prospective, observational data in the real world setting to contribute to the knowledge of palbociclib in ABC disease management and the new ABC treatment paradigm, and CCI [REDACTED]

[REDACTED] It is also of value to understand patient quality of life and the utility of geriatric assessment (GA) screening tools in treatment outcome measures of older breast cancer patients to further inform treatment decisions.

7. RESEARCH QUESTIONS AND OBJECTIVES

The objectives of this prospective NIS of palbociclib in ABC treatment are to describe and analyze palbociclib prescribing and treatment patterns in routine clinical practice, clinical outcomes, MBC treatment sequencing prior to, during, and after palbociclib, patient quality of life, geriatric specific assessment; and CCI [REDACTED]

[REDACTED]

The main research questions to be addressed may include the following:

- Palbociclib prescribing and treatment patterns in routine clinical practice in ABC treatment
- Clinical outcomes
- MBC treatment sequence
- Patient quality of life, as measured by EORTC QLQ-C30
- Geriatric Assessments in patients equal to or greater than 70 years of age at enrollment

CCI [REDACTED]

[REDACTED]

[REDACTED]

[REDACTED]

8. RESEARCH METHODS

8.1. Study Design

This is a prospective, non-interventional (NI), multicenter study being conducted in the US and CAN. The primary goal is to understand palbociclib prescribing and treatment patterns for patients with ABC being treated in routine clinical practice in the US and CAN.

Approximately 1,500 subjects will be enrolled across approximately 100 sites in the US and 10 sites in CAN. Study duration will consist of observation of patients on palbociclib treatment and approximately 3 years of follow-up post each patient's end of treatment with palbociclib, or until patient withdrawal from the study or death.

Participation in this study is not intended to change the routine treatment patients receive, as determined by their prescribing physicians; all treatment decisions, type and timing of disease monitoring are at the discretion of treating physician and patient.

Assessments include patient questionnaires and quality of life (EORTC QLQ-C30, G8 Screening Tool, ADL), site questionnaires, physician MBC treatment selection survey, and **CCI** [REDACTED], as detailed in Section 8.3 and Section 8.4.

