
0.6%), anemia (2.6% vs. 1.7%), thrombocytopenia (2.3% vs. 0%), and fatigue (2.0% vs. 1.2%). Febrile neutropenia was reported in 0.6% of patients in each treatment group. The rate of discontinuation due to AEs was 2.6% vs. 1.7%.¹⁵

Estrogen receptor – positive breast cancer is biologically heterogeneous. Although palbociclib clinical trial results are very promising, it is also recognized that not all patients may respond to palbociclib treatment, and palbociclib treatment does come with mechanism-based toxicities. **CCI**

16

Palbociclib is a novel CDK4/6 inhibitor approved in the US and CAN in combination with certain endocrine therapies for HR+/HER2 - ABC. With the introduction of this first in a new class of drugs, it is important to understand palbociclib treatment patterns in routine clinical practice in the US and, as a result, the evolving treatment landscape of ABC. It is important to understand real-world practice patterns and patient-reported outcomes as clinical trial populations may not be representative of real-life populations of patients given the preselection criteria and specific focus on a single line of therapy (LOT). This study will provide prospective observational data in real-world setting to contribute to the knowledge of palbociclib in ABC disease management and the new ABC treatment paradigm, CCI

[REDACTED]. It is also of value to understand patient quality of life and the utility of geriatric assessment screening tools in treatment outcome measures of older breast cancer patients.

STUDY DESIGN

Protocol A5481082 is a prospective non-interventional (NI) multicentre study being conducted in the US and Canada (CAN). The primary goal is to understand palbociclib prescribing and treatment patterns for patients with Advanced Breast Cancer (ABC) being treated in routine clinical practice in the US.

Approximately 1,500 patients will be enrolled – patient inclusion and exclusion criteria are itemized in Sections 8.2.1 and 8.2.2, respectively, of protocol A5481082 – across approximately 100 sites (community and academic) in the US and 10 sites in CAN. Study duration consists of observations of patients on palbociclib treatment and approximately 3 years of follow-up after each patient’s end of treatment with palbociclib, or until patient withdrawal from the study or death.

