8.8.1 Adverse Events

All safety analyses will be completed following Pfizer safety analysis standards, including descriptive statistics on all safety endpoints for the FAS. AEs will be monitored throughout the study duration. If the type and/or number of AEs warrants further examination, interim analyses will be conducted to determine whether those experiencing AEs are systematically different from other study participants. If the percentage of patients withdrawing from the study exceeds 25%, interim analyses will be conducted to examine whether systematic differences exist between those withdrawing from the study and those that continue with palbociclib treatment. Descriptive statistics comparing women and men who complete follow-up with those who withdraw from the study will also be completed to determine whether there are any systematic (demographic, clinical) differences between these such defined groups.

Descriptive statistics will be presented for all AEs and will be examined by AE grade. The incidence of all-cause and treatment-related AEs and SAEs separately will be reported. Specifically, a summary of incidence will be presented for the following variables:

- Patients evaluable for AEs
- Number of AEs
- Patients with AEs

PFIZER CONFIDENTIAL

- Patients with SAEs
- Number of SAEs
- Patients with Grade 3 or 4 AEs
- Patients with Grade 5 AEs
- Patients permanently discontinued study associated with AEs
- Patients permanently discontinued study associated with SAEs
- Patients permanently discontinued treatment associated with AEs
- Patients permanently discontinued treatment associated with SAEs
- Patients temporarily discontinued treatment associated with AEs
- Patients temporarily discontinued treatment associated with SAEs
- Patients with dose reduction associated with AEs
- Patients with dose reduction associated with SAEs
- Deaths

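### Data collection ending on 16Dec2021 cannot give each patient about 3 years of follow-up after palbociclib, and the SAP does not separate patients cut off by study closure

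*Protocol*

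**What the plan says.** - **Follow-up.** Protocol 8.1 describes observation on palbociclib followed by "approximately 3 years of follow-up post each patient's end of treatment with palbociclib, or until patient withdrawal from the study or death". Protocol 3 says the same. The SAP Study Design repeats it: "approximately 3 years of follow-up after each patient’s end of treatment with palbociclib". Withdrawal and death are the only stated reasons for a shorter period.
- **Calendar.** Protocol 5 (Milestones) plans data collection from 16Dec2016 to 16Dec2021 and the final report for 15NOV2022.
- **Accrual.** Protocol 8.1: "Approximately 1,500 subjects will be enrolled across approximately 100 sites in the US and 10 sites in CAN". Neither document gives an accrual period or a last-patient-in date. The 02AUG2017 entry in Protocol 4 reads "Study amended to include Canada for participation", so sites were still being added 7.5 months after the planned start.
- **Time on drug.** Protocol 6.2 reports for the first-line phase 3 trial "The median PFS was 24.8 months with palbociclib + letrozole", and for the phase 1/2 trial "The median PFS was 20.2 months with palbociclib + letrozole". After relapse or progression on endocrine therapy, the median PFS with palbociclib plus fulvestrant is 9.2 months.
- **Analyses that depend on follow-up.** Treatment sequence after palbociclib is an objective (Protocol 7, SAP Study Objectives). The Study Drug Exposure part of SAP section 8 reports each sequence pattern as a simple proportion of all patients. SAP 8.8.1 plans "Descriptive statistics comparing women and men who complete follow-up with those who withdraw from the study" without defining completion. SAP Appendix 1 sets the study end date at withdrawal or last contact, whichever is earlier, with no separate code for study closure.

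**The concern.** The milestone dates and the per-patient follow-up statement cannot both hold for every patient. The calendar cut-off is also unevenly distributed. A patient who stops palbociclib early has time for the full 3 years, while one who stays on it for a long time has little or none. How much post-palbociclib history is seen therefore depends on how long palbociclib lasted, which is itself an outcome.

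Two analyses are exposed. The completer comparison in SAP 8.8.1 has no defined place for a patient who neither withdrew nor reached 3 years. In the sequence table, a pattern that ends at palbociclib can mean three things: still on drug at data cut-off, stopped with no further line, or stopped too recently for the next line to be recorded. A raw proportion cannot tell these apart.

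**Working it through.** The plan gives no figure for the share of patients with full follow-up, so there is none to reproduce. The check starts from its dates.

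**Step 1: calendar.** 16Dec2016 to 16Dec2021 is 1826 days, or 60.0 months. 60 − 36 = 24 months remain for accrual plus time on palbociclib, so the last dose must fall by 16Dec2018. A patient enrolled on 02AUG2017 has 16.5 months. A patient enrolled after 16Dec2018 cannot reach 36 months.

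**Step 2: day-one enrolment, the most favourable case.** Assume exponential time on drug with the protocol's PFS medians *m* as proxy. The chance of stopping within 24 months is 1 − 2^(−24/*m*): 49% (*m* = 24.8), 56% (20.2), 84% (9.2).

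**Step 3: spread accrual.** Assume uniform enrolment over *A* months and ignore deaths and withdrawals. With λ = ln 2/*m*, the share able to reach 36 months is the mean over *u* in [0, *A*] of 1 − exp(−λ(24 − *u*)) for *u* < 24, and 0 otherwise.

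Example, *m* = 24.8 and *A* = 24: 24λ = 0.671 and exp(−0.671) = 0.511, so the share is 1 − (1 − 0.511)/0.671 = 0.271. For *A* = 36 it is 0.271 × 24/36 = 0.181.

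| Median on drug (months) | Able to reach 36 months, A = 12/24/36 | Median time on drug of those patients (months) | Stopped by 16Dec2021, so some post-drug observation |
|---|---|---|---|
| 24.8 | 39/27/18% | 7.8/6.0/6.1 | 78/73/68% |
| 20.2 | 46/32/21% | 7.6/5.8/5.9 | 84/80/75% |
| 9.2 | 73/54/36% | 6.1/4.7/4.7 | 98/97/94% |

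**Step 4: count death as completed follow-up.** The documents give no survival after palbociclib, so medians of 18 and 30 months are assumed. Share completing (one minus the simulated share cut off by the calendar), for *A* = 12/24/36:
- *m* = 24.8: 59/51/43% (18 months) and 53/44/35% (30 months).
- *m* = 9.2: 88/79/69% and 84/72/59%.

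**Step 5: skew in what is seen after palbociclib.** Among patients with any post-palbociclib observation, the share who stopped before the overall median would be 50% without skew. At *A* = 24 it is 0.50/0.734 = 68% (*m* = 24.8), 0.50/0.802 = 62% (20.2) and 0.50/0.969 = 52% (9.2). Across *A* = 12 to 36 the ranges are 64–74%, 59–67% and 51–53%.

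**Step 6: window needed.** For the last patient enrolled, with median time on drug, it is *A* + *m* + 36 months. With *m* = 24.8 that is 72.8, 84.8 and 96.8 months for *A* = 12, 24 and 36, and 60.8 even with *A* = 0. The planned 60 months suffices only if *A* ≤ 3.8 (*m* = 20.2) or *A* ≤ 14.8 (*m* = 9.2).

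**The case against.** The strongest reply is that little is damaged in practice. The milestones are planned dates and the follow-up is stated as approximate. The study is descriptive and hypothesis-generating (Protocol 8.9, SAP section 8). rwPFS and OS use Kaplan-Meier with censoring, and follow-up time is reported overall and by line. The completer comparison is an attrition check, not an objective. The raw material for a closure category is largely collected: data are entered at end of study (Table 1, footnote 2), Protocol 9.2 allows withdrawal for administrative reasons, and the SAP lists completion dates and reasons for premature termination. The SAP cites 2020 case estimates and discusses COVID, so it was evidently written well after 16Dec2018. It still repeats the 3 years, so the milestone may be the stale item.

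Much of this stands. The survival endpoints are not affected, and the documents do not show which statement is out of date. But the word approximate cannot absorb a shortfall of a year or more, and collecting the reason for study end does not assign closed-out patients to a group in SAP 8.8.1.

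Three stronger readings are tempting and should be resisted:
- **That post-palbociclib sequences would mainly describe early stoppers at every line.** Under 24-month accrual, 73% (median 24.8) and 97% (median 9.2) have some post-palbociclib observation, and 63% and 92% have at least 12 months available. The skew is moderate at the first-line medians and slight at 9.2 months.
- **That typical first-line follow-up is about 22 months.** That median counts patients still on palbociclib as zero. Among those who stop, median potential follow-up is about 31 months at 24-month accrual with the 24.8-month median (36 and 26 months at 12- and 36-month accrual).
- **A single figure for the whole cohort.** It needs a first-line to later-line mix, which the documents do not give.

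**Conclusion.** The concern holds as a conflict between the planned dates and the stated follow-up, with two consequences of limited reach. The 24-month limit is plain arithmetic and needs no assumption.

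The size of the shortfall rests on assumed uniform accrual, exponential time on drug and PFS as a proxy. Stopping for toxicity (9.7% permanent discontinuation for adverse events in the first-line phase 3 trial) or enrolling patients already on palbociclib (Table 1, footnote 8) would raise the shares. On these assumptions, with deaths and withdrawals ignored, fewer than half can reach 3 years at either first-line median for any accrual period of 12 to 36 months. At the 9.2-month median the share runs from 73% down to 36%. Counting deaths as completion narrows the gap but leaves 41–65% cut off by the calendar at the 24.8-month median and 12–41% at 9.2 months.

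The group of survivors who complete 3 years is therefore selected for early stopping. For treatment sequence, full sequences and later lines are affected most. The first subsequent line should be seen for most patients who stop within the window.

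**What to change.** 1. **Reconcile Protocol 5 with Protocol 3, Protocol 8.1 and the SAP Study Design.** Either move the end-of-collection milestone, or restate follow-up as running to about 3 years after the end of palbociclib or to the end of data collection, whichever comes first, unless withdrawal or death intervenes. State the accrual period as well.
2. **In SAP 8.8.1, define complete follow-up and use three groups:** reached 3 years or died; ended by study closure; withdrew. Carry the closure category into the disposition summary.
3. **In the SAP Study Drug Exposure section, keep the sequence table for all patients,** since restricting it to those who stopped would condition on the same selection. Show patients still on palbociclib at data cut-off as their own category. Give the numbers with at least 12, 24 and 36 months of potential post-palbociclib follow-up. Report the start of each next line by cumulative incidence or another method that allows for censoring.

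Cost: text changes, one extra disposition category and a little more analysis. The stated follow-up becomes less favourable if the dates stay. No new data are needed unless the sponsor chooses to extend collection.
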